### 6.1 Definitions

Serious adverse event (SAE): any untoward medical occurrence that at any dose:

- Results in death,
- Is life threatening, (Note: the term "life-threatening" refers to an event/reaction in which the patient was at risk of death at the time of the event/reaction; it does not refer to an event/ reaction which hypothetically might have caused death if it were more severe),
- Requires inpatient hospitalization or results in prolongation of existing hospitalization,
- Results in persistent or significant disability/incapacity,
- Is a congenital anomaly/birth defect, or
- Is a medically important event or reaction. Medical and scientific judgment should be exercised in deciding whether other situations should be considered serious, such as important medical events that might not be immediately life-threatening or result in death or hospitalization, but might

jeopardize the patient or might require intervention to prevent one of the other outcomes listed in the definition above.

**Related Adverse Event, i.e. Adverse Drug Reaction (ADR):** There is a reasonable possibility per the IST/ISS sponsor that the product may have caused the event.

**Unexpected Adverse Drug Reaction:** An adverse reaction, the nature or severity of which is not consistent with the applicable product information (e.g., Investigator's Brochure for an unapproved investigational product or package insert/summary of product characteristics for an approved product). An expected ADR with a fatal outcome should be considered unexpected unless the local/regional product labeling specifically states that the ADR might be associated with a fatal outcome.

## **6.2 Management of Study Drug Events and Drug Dosing Modifications**

Any patient who receives treatment on this protocol will be evaluated for toxicity. Each patient will be assessed for the development of toxicity. Toxicity will be assessed per the NCI Common Toxicity Criteria for Adverse Events (CTCAE), version 4.03. Dose adjustments should be made according to the system showing the greatest degree of toxicity. Concurrent participation in another clinical trial or treatment with any other anti-cancer therapy is not permitted. The Investigator may prescribe any other concomitant medications as deemed necessary.

The proposed dosing of 5-AZA is based on the FDA-approved doses for MDS. 5-azacitidine is generally well tolerated, as demonstrated by a phase II trial in chemo-naive castration-resistant metastatic prostate cancer. The toxicities were generally mild and manageable and only 4 out of 36 patients discontinued therapy due to toxicities. ATRA has been studied in multiple phase II trials of PCa patients. In both studies, the toxicities were mild and manageable. Only one patient required dose reduction in each trial.

Sequential boundaries will be used to monitor the toxicity rate. In this trial, we conservatively plan that the accrual will be halted if there is sufficient evidence that the toxicity rate exceeds the acceptable rate of 10% by more than 15% (unacceptable toxicity rate of 25%). The discrete toxicity boundary values are reported in following Table 4. The cumulative number of patients experiencing the toxicities described in Table 6 and 7 will be compared with Pocock's stopping boundary values and if greater than the associated boundary value, then the trial will stop early. This toxicity monitoring plan controls the overall type I error rate of 10%, i.e., probability of stopping trial early under acceptable toxicity rate of 10%, and 80% power, i.e., probability of stopping trial early under unacceptable toxicity rate of 25%.

Table 4: Progressive toxicity boundary rules for cumulative number of patients experiencing toxicity.

Looks	5	10	15	20
Boundary	1	2	3	4

If among the 20 patients, 2 or more of the first 5, 3 or more of the first 10, 4 or more of the first 15, or 5 or more of the first 20 patients experience recurrent grade 3 or 4 hematological or non-hematological toxicities defined in Table 6 and 7 or any toxicity deemed unacceptable by the patient or investigator during the 12-week treatment window and up to 4 weeks after treatment window, we will stop the trial early.

The statistical operating characteristics of the above toxicity monitoring rule are as follows:

Table 5: Probability of stopping early based on the true toxicity rate.

Toxicity probability	10%	13%	16%	19%	22%	25%
----------------------	-----	-----	-----	-----	-----	-----

Early stopping probability	14%	24%	36%	48%	60%	71%
----------------------------	-----	-----	-----	-----	-----	-----

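### Section 6.2 claims 10% type I error and 80% power for the toxicity stopping rule; its own Table 5 gives 14% and 71%, and no rule on 20 patients can deliver both claimed figures.

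*Combined protocol and SAP*

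**What the plan says.** Section 6.2 sets an acceptable toxicity rate of 10% and an unacceptable rate of 25%. Accrual is to be halted on sufficient evidence that the rate "exceeds the acceptable rate of 10% by more than 15% (unacceptable toxicity rate of 25" percent).

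The rule is given twice in that section, and the two versions agree:

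- Table 4 has looks at 5, 10, 15 and 20 patients with the row "Boundary 1 2 3 4". The text says of the cumulative count that "if greater than the associated boundary value, then the trial will stop early".
- The paragraph after Table 4 puts this in words: "2 or more of the first 5, 3 or more of the first 10, 4 or more of the first 15". At the fourth look, with 20 patients, the trial stops on a count of 5 or higher.

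The properties of the rule are also given twice, and here the two versions differ:

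- The prose before Table 4: "This toxicity monitoring plan controls the overall type I error rate of 10" percent, and "80% power, i.e., probability of stopping trial early under unacceptable toxicity rate of 25" percent.
- Table 5, headed "Table 5: Probability of stopping early based on the true toxicity rate" and introduced as describing the rule just given: 14, 24, 36, 48, 60 and 71% at true rates of 10, 13, 16, 19, 22 and 25%.

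**The concern.** The prose and Table 5 report the same two quantities for the same rule at the same true rates, and they disagree: 10% against 14%, and 80% against 71%. The prose spells out what it means by type I error and by power, in each case a probability of stopping early, so a difference in definition cannot explain the gap. Nothing in the document says which statement governs.

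Safety is a co-primary objective (section 2.1), and the safety analysis in section 8.4 is otherwise descriptive. The stopping rule is therefore the only trial-level quantitative safety threshold in the plan. Section 2 adds that, to the authors' knowledge, the combination has not been studied before in recurrent prostate cancer. A reader who relies on the prose will believe that the rule misses an unacceptable toxicity rate one time in five and stops a tolerable regimen one time in ten.

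**Working it through.** **Inputs** (all from section 6.2): acceptable rate p0 = 0.10; unacceptable rate p1 = 0.25; looks after 5, 10, 15 and 20 patients; stop if the cumulative count exceeds 1, 2, 3 or 4 respectively. Assumption: patients' toxicity outcomes are independent with a common rate p.

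**Step 1. Exact stopping probability of the written rule.** Carry forward the distribution of the count among trials not yet stopped, add five new patients by the binomial formula, and remove the probability above the boundary.

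*Look 1, p = 0.10.* P(2 or more of 5) = 1 − 0.9^5 − 5(0.1)(0.9^4) = 1 − 0.59049 − 0.32805 = 0.0815.

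*Look 2, p = 0.10.* Trials that continue have 0 events (0.59049) or 1 event (0.32805). To reach 3 they need 3 or more, or 2 or more, of the next five: 0.59049 × 0.00856 + 0.32805 × 0.08146 = 0.0318.

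Looks 3 and 4 follow in the same way:

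| True rate | Look 5 | Look 10 | Look 15 | Look 20 | Total |
|---|---|---|---|---|---|
| 10% | 0.0815 | 0.0318 | 0.0157 | 0.0088 | 0.1378 |
| 25% | 0.3672 | 0.1698 | 0.1007 | 0.0675 | 0.7052 |

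**Step 2. Compare with Table 5.**

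| True rate | 10% | 13% | 16% | 19% | 22% | 25% |
|---|---|---|---|---|---|---|
| Table 5 | 14% | 24% | 36% | 48% | 60% | 71% |
| Exact | 13.8% | 23.9% | 35.7% | 48.1% | 60.0% | 70.5% |

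Every Table 5 entry is reproduced to the rounded percent.

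**Step 3. Look for a reading that gives 10% and 80%.**

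| Reading | Stop at 10% | Stop at 25% |
|---|---|---|
| As written | 13.8% | 70.5% |
| Stop when the count equals or exceeds the boundary | 48.6% | 91.4% |
| Count only the first three looks as early | 12.9% | 63.8% |
| Monitor after every patient, same boundaries | 13.8% | 70.5% |
| Single look, 5 or more of 20 | 4.3% | 58.5% |
| Single look, 4 or more of 20 | 13.3% | 77.5% |

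None does.

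**Step 4. Could another boundary meet both figures with 20 patients?** Any stopping rule on 20 independent outcomes is a test of 10% against 25%, so the Neyman-Pearson lemma bounds its power by that of the most powerful (randomised) test of the same size.

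- *Error fixed at 10%.* Under p0, P(X ≥ 5) = 0.0432 and P(X = 4) = 0.1330 − 0.0432 = 0.0898. The test rejects at X = 4 with probability (0.10 − 0.0432)/0.0898 = 0.633. Its power is 0.5852 + 0.633 × (0.7748 − 0.5852) = 0.705.
- *Power fixed at 80%.* Under p1, P(X ≥ 4) = 0.7748 and P(X = 3) = 0.9087 − 0.7748 = 0.1339. The test rejects at X = 3 with probability (0.80 − 0.7748)/0.1339 = 0.188. Its error is 0.1330 + 0.188 × (0.3231 − 0.1330) = 0.169.

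So 10% error allows at most 70.5% power, and 80% power needs at least 16.9% error. A search over non-decreasing boundaries at the four planned looks agrees. The best power with error no more than 10% is 67.6% (stop above 2/2/3/4), and the lowest error with power of at least 80% is 18.5% (stop above 1/2/3/3). For scale, the smallest single-look rule that meets both figures needs 31 patients (6 or more events: error 8.3%, power 82.4%).

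**The case against.** The strongest reply is that nothing is hidden. Table 5 follows almost at once, gives the correct figures in more detail than the prose, and the operative rule is unambiguous. Correcting the sentence changes no boundary or analysis, so this is an internal inconsistency rather than a defect in the monitoring itself. That is a fair account of its nature, and the harm should not be put more strongly. But Table 5 is one half of the contradiction and cannot also excuse it. A sentence saying that the plan controls a 10% error is false when the rule's error is 13.8%.

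A second reply is that 20 may not be the cap. Section 8.2 replaces patients who do not finish 8 weeks of treatment but still counts them for the toxicity rule, so more than 20 could be counted. The theoretical power bound at 10% error rises to 78.8% with 25 patients and just passes 80% with 28. The impossibility statement is therefore confined to 20 patients. This does not rescue the claim for the plan as written: section 6.2 defines no boundary beyond 20, so further patients add no chance of stopping, and Table 5 is reproduced exactly at 20.

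A third reply is that the documents do not show whether the sponsor meant this boundary or meant the 10% and 80% targets and derived the boundary wrongly. That stands, and it is for the sponsor to say. On either reading the sentence cannot remain beside Table 5.

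**Conclusion.** The concern holds. For the rule as written, the probability of stopping is 13.8% at a 10% toxicity rate and 70.5% at 25%, not 10% and 80%. The false-stop risk is 13.8/10, or about 1.4 times the stated value. The risk of not stopping at 25% is 100 − 70.5 = 29.5%, against the 20% implied by the text, which is nearly half as much again. Both misstatements favour the design.

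The mismatch with Table 5 is visible on the page and needs no assumption. The exact figures assume independent outcomes with a common toxicity rate and monitoring that ends at 20 patients; agreement with all six entries indicates that Table 5 was computed on the same basis. No view is taken here on which stopping boundary is clinically appropriate.

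**What to change.** In section 6.2, replace the sentence on type I error and power with the properties of the rule as written: a probability of stopping of about 14% if the true toxicity rate is 10%, and about 71% if it is 25%. Delete the statement that the plan controls a 10% error with 80% power, so that prose and Table 5 agree.

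The cost is one sentence and less favourable figures. Tables 4 and 5, the sample size and patient management are untouched.

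If the sponsor in fact wants 10% and 80%, rewording will not achieve it, because 20 patients cannot supply both; the rule and the number monitored would have to be reconsidered. A note in the protocol that the pair is unattainable at 20 patients would be helpful but is optional.

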### 6.2.1 Hematologic Toxicities

**Table 6. Hematologic toxicity dose reductions for 5-AZA**

Grade	ANC a	Platelets	Hemoglobin	Action
1	<LLN to 1,500/ $\mu$ L	<LLN to 75,000/ $\mu$ L	< LLN to 10 g/dL	None
2	1000-1499/ $\mu$ L	50,000 to 74,999/ $\mu$ L	8 – 10 g/dL	None
3	500-999/ $\mu$ L	25,000 to 49,999/ $\mu$ L	< 8 g/dL	
-1st Occurrence: Hold current dose until ANC <math>\geq</math> 1,000/<math>\mu</math>L, platelets <math>\geq</math> 50,000/<math>\mu</math>L, and hemoglobin <math>\geq</math> 8 g/dL. Do not replace missed doses. Restart next treatment at 30 mg/m^2 dose.
 
-2nd Occurrence: Discontinue protocol therapy.
 
-If therapy held > 3 weeks: Discontinue protocol therapy.

4	<500/ $\mu$ L	<25,000/ $\mu$ L	Life-threatening consequences; urgent intervention indicated	
-1st Occurrence: Hold current dose until ANC <math>\geq</math> 1,000/<math>\mu</math>L, platelets <math>\geq</math> 50,000/<math>\mu</math>L, and hemoglobin <math>\geq</math> 8 g/dL. Do not replace missed doses. Restart next treatment at 30 mg/m^2 dose.
 
-2nd Occurrence: Discontinue protocol therapy.
 
-If therapy held > 3 weeks: Discontinue protocol therapy.

aNote: G-CSF (Filgrastim) 5 mcg/kg/day may be added for low ANC on day of treatment BEFORE a dose reduction is instituted at treating physician's discretion. This will be continued until anticipated nadir has passed and ANC <math>\geq</math> 1000. Neulasta® is NOT allowed.
				

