### 6.2.2 Non-hematologic toxicities

5-AZA will be continued at the original dose if the adverse event is grade 0-2. For grade 3-4 toxicities related to study drug, 5-AZA will be held until improvement of symptoms to grade 2 or below. After the first episode, the dose will be reduced by 25%. After the second episode, the protocol therapy will be discontinued. The investigator will determine whether the toxicity is related to study drug. The investigator may prescribe any concomitant medications as necessary, except for other anti-cancer therapy, for the management of adverse effects.

ATRA will be continued at the original dose if the adverse event is grade 0-2. For grade 3-4 toxicities related to study drug, ATRA will be held until improvement of symptoms to grade 2 or below. After the first episode,

the dose will be reduced by 25%. After the second episode, the protocol therapy will be discontinued. The investigator will determine whether the toxicity is related to study drug. The investigator may prescribe any concomitant medications as necessary, except for other anti-cancer therapy, for the management of adverse effects.

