**Table 7. Non-hematologic toxicity dose reductions for 5-AZA and ATRA**

NCI CTC Grade	5-AZA	ATRA
0-2	No change from original starting dose	No change from original starting dose
3 -4	Hold until resolved to $\leq$ Grade 2, then reduce to 30 mg/m^2	Hold until resolved to $\leq$ Grade 2, then reduce to 34 mg/m^2
Second episode of grade 3 or 4 toxicity	Remove subject from trial	Remove subject from trial

The administration of 5-AZA will be reported in a log book by the clinical trial staff. All patients will receive a study medication diary to log medication administration and adverse events for both 5-AZA and ATRA (See Appendix A).

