## **8. STATISTICAL CONSIDERATIONS**

### **8.1 Study Design/Study Endpoints**

The primary endpoints will be the disease progression-free rate at the end of the treatment phase 1 and safety of the combination of 5-AZA and ATRA. Disease progression is defined by composite of PSA or radiographic progression relative to period baseline (start of treatment phase 1), whichever occurs first. PSA levels will be measured on day 1 of each cycle. For assessment of PSA progression, see section 3.2.1 above. CT A/P and bone scan will be performed every 3 cycles. For assessment of radiographic progression, see section 3.2.2 above. Safety will be assessed by the recording of adverse events, monitoring of vital signs and physical examinations, safety laboratory evaluations, and 12-lead ECG. Adverse events will be graded per the Common Terminology Criteria for Adverse Events (CTCAE) version 4.0. Therapy will be continued at the original dose if the adverse event is grade 0-2. For grade 3-4 toxicities, therapy will be held until improvement of symptoms to grade 2 or below. The dose will then be reduced by 25% of original for each episode. A maximum of 2 dosage reductions will be allowed. The third occurrence will result in removal of the patient from the study.

The secondary endpoints will be time to tumor progression from start of treatment phase 1 and the measurement of dormancy biomarker levels in relation to disease states: tumor progression and disease progression. To determine the relation between dormancy biomarkers and disease states, every 3 cycles, we will measure the dormancy biomarkers, TGF $\beta$ 2, BMP7, BMP4, GAS6, retinoic acid, NR2F1, in BM aspirates and peripheral blood.

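### Section 8.1 re-doses a patient after a second grade 3–4 toxicity where section 6.2 ends therapy, and section 6.2 words the stopping-rule event in two ways

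*Combined protocol and SAP*

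**What the plan says.** **Dose rules for one patient.** Section 8.1 lowers the dose by a quarter of the original at each grade 3–4 episode and adds: "A maximum of 2 dosage reductions will be allowed". It then says: "The third occurrence will result in removal of the patient from the study".

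Section 6.2 has a different rule in three places:
- Table 6 (hematologic toxicity, 5-AZA) holds treatment at the first grade 3 or 4 occurrence and restarts at 30 mg/m². At the second occurrence the instruction is "Discontinue protocol therapy".
- Section 6.2.2 gives one 25% reduction after the first episode, separately for 5-AZA and ATRA. It then states for each: "After the second episode, the protocol therapy will be discontinued".
- Table 7 reduces 5-AZA to 30 mg/m² and ATRA to 34 mg/m². Its row labelled "Second episode of grade 3 or 4 toxicity" takes the subject off the trial.

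Section 7.1 asks that patients taken off be followed per protocol.

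**Stopping rule for the trial.** The paragraph of section 6.2 before Table 4 sets an acceptable toxicity rate of 10% and an unacceptable rate of 25%. It compares the following with boundaries of 1, 2, 3 and 4 at 5, 10, 15 and 20 patients, stopping if the count is greater: "The cumulative number of patients experiencing the toxicities described in Table 6 and 7". The paragraph after Table 4 stops at 2 of 5, 3 of 10, 4 of 15 or 5 of 20 patients who "experience recurrent grade 3 or 4 hematological or non-hematological toxicities defined in Table 6 and 7 or any toxicity deemed unacceptable by the patient"; the investigator may also make that judgement. Events count within the 12-week treatment window plus 4 weeks. Table 5 is then introduced with "The statistical operating characteristics of the above toxicity monitoring rule are as follows".

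**The concern.** Safety is a co-primary endpoint, and section 2 says the investigators know of no earlier study of this combination in recurrent prostate cancer. The rules for taking a patient off drug and for stopping the trial should therefore each have one meaning.

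On dosing, a second grade 3–4 event is where the two sections part. One investigator could continue at a further reduced dose and another could stop treatment, and each could point to the protocol.

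On stopping, the boundary is fixed but the thing counted is worded in two ways. If the difference is noticed only when a count is close to a boundary, the choice of wording would be made with the results in view.

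**Working it through.** **1. Dosing rules side by side**

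| Grade 3–4 event | Table 6, section 6.2.2, Table 7 | Section 8.1 |
|---|---|---|
| First | Hold, then reduce by 25% | Hold, then reduce by 25% of original |
| Second | Therapy ends | Hold, then reduce by a further 25% of original |
| Third | Not reached | Patient removed |

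Doses implied by each rule, from starting doses of 40 mg/m² (5-AZA) and 45 mg/m² (ATRA):
- First reduction: 40 × 0.75 = 30 mg/m²; 45 × 0.75 = 33.75, which Table 7 gives as 34 mg/m². All sources agree here.
- Second reduction, section 8.1 only: 40 × 0.50 = 20 mg/m²; 45 × 0.50 = 22.5 mg/m². Neither table has such a dose level.

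The rules agree at the first event and conflict at the second. The end state also differs in wording: Table 6 and section 6.2.2 discontinue therapy, whereas Table 7 and section 8.1 remove the patient from the trial or study.

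**2. Stopping rule side by side**

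| Element | Before Table 4 | After Table 4 |
|---|---|---|
| Boundary | More than 1, 2, 3, 4 | At least 2, 3, 4, 5 (identical) |
| Event | Toxicities described in Tables 6 and 7 | Toxicities defined in Tables 6 and 7 |
| Grade | Not stated | 3 or 4 |
| Recurrence | Not required | Required |
| Toxicity deemed unacceptable | Not mentioned | Counts |
| Window | Not stated | 12 weeks plus 4 |

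Table 6 also lists grades 1 and 2, with no action. The sensible reading of the first paragraph is therefore grade 3–4. On that reading, two first-time grade 3–4 events among the first five patients cross the boundary under the first paragraph. Under the second they do so only if each is deemed unacceptable. *Recurrent* itself is not obscure: Table 6, Table 7 and section 6.2.2 all separate a first episode from a second. Section 8.2, the only other mention of the rule, says which patients are included, not which event counts.

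**3. Does Table 5 settle which event is meant?**

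Let p be the per-patient probability of the counted event and C(n) the cumulative count after n patients, with five new patients per look. Then

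P(stop) = 1 − P(C(5) ≤ 1, C(10) ≤ 2, C(15) ≤ 3, C(20) ≤ 4).

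| True rate p | 10% | 13% | 16% | 19% | 22% | 25% |
|---|---|---|---|---|---|---|
| Table 5 | 14% | 24% | 36% | 48% | 60% | 71% |
| Recomputed | 13.8% | 23.9% | 35.7% | 48.1% | 60.0% | 70.5% |

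At p = 0.25 the first look gives 1 − 0.75⁵ − 5 × 0.25 × 0.75⁴ = 0.367. The four looks add to 0.3672 + 0.1698 + 0.1007 + 0.0675 = 0.7052.

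All six values reproduce, which confirms the boundaries. The formula contains only p, so Table 5 fits either event equally well and cannot identify the one intended.

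**The case against.** On dosing, section 6.2 is the dose-modification section. Its three statements agree and name the reduced doses, while section 8.1 is a recap inside the statistics. Staff would probably follow section 6.2. That stands as evidence of intent, and it is why section 8.1 is the text to change. It does not remove the conflict: section 8.1 is unqualified current text, and nothing ranks the two sections.

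On stopping, the objection is stronger. The paragraphs are consecutive and cite the same tables. The second supplies the grade and window that the first needs before it can be applied, and it leads into Table 5. The paragraph just before the rule cites 4 of 36 patients discontinuing 5-AZA for toxicity (11%). That is close to the 10% acceptable rate and fits an event severe enough to end therapy, as a second grade 3–4 episode is; this is inference, not a stated link. Most of this stands. A reader might infer two rival stopping rules with nothing to choose between them, and the text does not support that. What remains is that the first paragraph is itself worded as a decision rule and carries the 10% and 25% rates. The second is also more than an elaboration: it both narrows the event (recurrence) and widens it (the unacceptable-toxicity clause), without saying that it governs.

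**Conclusion.** The point holds with two parts of unequal weight. The main one is the contradiction over a second grade 3–4 event: re-dose, at an implied 20 mg/m² of 5-AZA or 22.5 mg/m² of ATRA, or end therapy. This rests on the text alone. The lesser one is the loose statement of the counted event, where the paragraph after Table 4 is probably operative.

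A reader might go further and infer that the recurrence condition cuts the chance of stopping. Suppose 25% of patients have a first grade 3–4 event, and 25%, 50% or 75% of them are counted under the later paragraph. The counted rates are then 6.25%, 12.5% and 18.75%, with stopping probabilities of 5%, 22% and 47% against 71%. These figures do not measure the defect. They read the same curve at assumed lower rates, and they attach the 25% to first events when the protocol attaches it to whatever toxicity is counted. The direction is not fixed either. Adding an independent 5% rate of unacceptable toxicity to a 10% counted rate gives 1 − 0.90 × 0.95 = 14.5%, and raises stopping from 13.8% to 29.6%. The documents give neither a recurrence rate nor a rate of unacceptable toxicity, so the effect on stopping cannot be determined.

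Nor do the documents support a reading that patients are unprotected. Every version holds and reduces at the first grade 3–4 event, and the unacceptable-toxicity clause lets a worrying first event count. The point should be fixed because it bears on safety decisions and the correction is cheap.

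**What to change.** 1. **Section 8.1:** allow one 25% dose reduction. At the second grade 3–4 episode, discontinue protocol therapy, with follow-up per protocol as in section 7.1. Delete the two-reduction and third-occurrence sentences.
2. **Table 7:** replace removal from the trial with discontinuation of protocol therapy, to match Table 6 and section 6.2.2.
3. **Section 6.2, paragraph before Table 4:** refer to the event as defined below, so that the definition after Table 4, with its 12-week plus 4-week window, is the only one.
4. **Section 6.2, paragraph after Table 4:** state that *recurrent* means a second grade 3–4 episode per Tables 6 and 7, and that the 10% and 25% rates and Table 5 refer to this event.

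The cost is a few sentences of protocol wording. Boundaries, Table 5 and sample size do not change.

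If the sponsor instead wants first grade 3–4 events to count, deleting *recurrent* is not a wording change. It alters the monitored event, so the 10% and 25% rates would need fresh justification. Section 5.1.5 reports grade 3 fatigue in 11.8% and grade 3 neutropenia in 5.9% on 5-AZA alone.
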